### **2.3.2 Safety population**

The safety population is defined as:

- Randomized population who received at least 1 dose or part of a dose of the IMP, analyzed according to the treatment actually received

In addition:

- Nonrandomized but treated participants will not be part of the safety population; however, their safety data will be presented separately
- Randomized participants for whom it is unclear whether they took the IMP will be included in the safety population as randomized according to their planned treatment

- For participants receiving 1 or more injections during the trial, the treatment group allocation for as-treated analysis will be included in the treatment group that they are exposed for longer duration. In case of tie, highest dose group of efpeglenatide will be used. When calculating the Dulaglutide treatment duration, the Dulaglutide 0.75 mg duration will be combined with Dulaglutide 1.5 mg
- Participants, who premature discontinued study treatment during the titration phase, will be summarized in their planned treatment group for as-treated analysis too.
- Randomized participants will be excluded from the safety population only if there is documented evidence (ie, all study dates recorded as no medication taken) that participants have not taken the study treatment. If a participant is dispensed IMP and is lost to follow-up without any documented evidence, the participant will be considered exposed.

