#### **2.4.3 Extent of investigational medicinal product exposure and compliance**

The extent of IMP exposure and compliance will be assessed and summarized by actual treatment within the safety population ([Section 2.3.2](#)).

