##### **2.4.3.1 Extent of investigational medicinal product exposure**

The extent of open-label IMP exposure will be assessed by cumulative exposure (patient years), duration (days), and category (weeks).

Duration of open-label IMP exposure is defined as last dose date – first dose date + 7, regardless of unplanned intermittent discontinuations (see [Section 2.5.3](#) for calculation in case of missing or incomplete data).

Duration of open-label IMP exposure will be summarized descriptively as a quantitative variable (number, mean, SD, median, minimum, and maximum). In addition, duration of treatment exposure will also be summarized categorically by numbers and percentages for each of the following categories and cumulatively according to these categories: 1 to 2 weeks, 3 to 4 weeks, 5 to 8 weeks, 9 to 12 weeks, 13 to 18 weeks, 19 to 24 weeks, 25 to 30 weeks, 31 to 43 weeks, 44 to 56 weeks, and >56 weeks. The duration of treatment exposure in weeks will be the duration (in days)/7, rounded to the nearest integer.

Duration of study will be summarized separately and analyzed descriptively as a quantitative variable (number, mean, SD, median, minimum, and maximum). The study duration is defined as date of completion or discontinuation – date of first open-label IMP + 1. If the date of first open-label IMP is missing, then the date of randomization will be used.

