***Analysis of all treatment-emergent adverse event(s) leading to treatment discontinuation***

- All TEAEs leading to treatment discontinuation, by primary SOC, HLGT, HLT, and PT, showing the number (%) of participants

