### **2.4.5.2 Analysis of Hypoglycemia**

Treatment-emergent hypoglycemia events will be tabulated separately from the AEs.

Event frequency and incidence of hypoglycemia events will be summarized by treatment for all reported hypoglycemia and per type of hypoglycemic event described in [Section 2.1.4.6](#) (ie, severe, documented symptomatic, asymptomatic, probable symptomatic, relative) for safety population. Incidence of severe or documented symptomatic hypoglycemia events will be summarized by study period ( $\leq 4$  weeks (titration period),  $> 4$  weeks to  $\leq 8$  weeks,  $> 8$  weeks to  $\leq 30$  weeks,  $> 30$  weeks) and according to time of occurrence (nocturnal [ie, 00:00 to 05:59 am], daytime [ie, 06:00 am to 23:59]) for safety population. Documented hypoglycemia (symptomatic or asymptomatic) will be also evaluated for the more stringent plasma glucose threshold of  $< 54$  mg/dL (3.0 mmol/L), as well as for  $\geq 3.0$  and  $< 3.9$  mmol/L ( $\geq 54$  and  $< 70$  mg/dL). Frequency and percentage of participants with at least one hypoglycemia event will be summarized as well.

Event rate of hypoglycemia per participant year will be calculated by treatment using the total number of hypoglycemia events from all participants (denoted as n) divided by the total exposures from all participants expressed in years (ie, participant exposure in days divided by 365.25, denoted as t). Multiple events from an individual participant will all be counted. Event rates of hypoglycemia per participant year {all reported hypoglycemia, severe, documented symptomatic [ $< 54$  mg/dL ( $< 3.0$  mmol/L),  $\geq 54$  and  $< 70$  mg/dL ( $\geq 3.0$  and  $< 3.9$  mmol/L),  $\leq 70$  mg/dL ( $\leq 3.9$  mmol/L) respectively], asymptomatic, probable symptomatic, relative hypoglycemia} will be presented by treatment group during the 56-week on-treatment period.

The summary of frequency and event rate in participant years for severe or documented symptomatic hypoglycemia will be provided as appropriate by gender (Male, Female), age group ( $< 50$ ,  $\geq 50$  to  $< 65$ ,  $\geq 65$  to  $< 75$ ,  $\geq 75$  years), and race (Asian, Black or African American, White, Other).

A KM curve will also be provided by treatment group for the time to first severe or documented symptomatic hypoglycemia during the on-treatment period.

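### SAP 2.3.2 adds dulaglutide's titration time to its target dose but has no matching rule for efpeglenatide, so a 6 mg participant who stops just after reaching 6 mg may be tabulated under 4 mg

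*SAP*

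**What the plan says.** SAP 2.3.2 analyzes treated participants by treatment actually received and makes longer exposure the deciding rule: "the treatment group allocation for as-treated analysis will be included in the treatment group that they are exposed for longer duration". Three further provisions qualify it.

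- Ties: "In case of tie, highest dose group of efpeglenatide will be used".
- Titration time, for one drug only: "the Dulaglutide 0.75 mg duration will be combined with Dulaglutide 1.5 mg".
- Early stoppers: "Participants, who premature discontinued study treatment during the titration phase, will be summarized in their planned treatment group for as-treated analysis too".

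Nothing says how efpeglenatide 2 mg and 4 mg injections given as titration are counted, and the section does not define the titration phase. Under the dose schedule in Protocol Table 2, the 6 mg arm receives 2, 2, 4, 4 and then 6 mg from Week 4. Protocol Section 6 reserves 2 mg for titration, so no 2 mg group exists.

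The grouping feeds the adverse event tables, including "All TEAEs leading to treatment discontinuation, by primary SOC, HLGT, HLT, and PT, showing the number (%) of participants". It also feeds exposure and compliance: "The extent of IMP exposure and compliance will be assessed and summarized by actual treatment within the safety population".

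**The concern.** The dulaglutide sentence is the less necessary of the two, because 0.75 mg is not a treatment group and its time has only one natural destination. Efpeglenatide 4 mg time in the 6 mg arm can be credited to either of two columns, and there the SAP gives no rule.

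If exposure is counted by dose level, the result is out of order. A 6 mg participant who never received 6 mg is reported under 6 mg by the titration exception. One who goes on to take a single 6 mg injection and then stops is reported under 4 mg. That second person is informative about tolerability of the step to 6 mg. Protocol Sections 2.3 and 4.3 describe nausea and vomiting as dose related, and Protocol 7.1.1 lists confirmed intolerance to the allocated dose as a reason to stop. Moving such people would tend to make 6 mg look better and 4 mg look worse in the as-treated tables.

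**Working it through.** The documents give no figure for this rule, so there is none to reproduce. The check applies the rule to the dose schedule.

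**Inputs**
- Weekly doses in the 6 mg arm: 2, 2, 4, 4 mg at Weeks 0 to 3, then 6 mg (Protocol Table 2).
- Visit 4 at Day 14 ±3 and Visit 5 at Day 28 ±3 (Protocol 1.3).
- Seven days credited for the last dose, as in the overall exposure formula of SAP 2.4.3.1. Applying this at each dose level is an assumption, since the SAP does not define duration per dose.
- Longer-exposure, tie and titration rules from SAP 2.3.2.

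**Compliant participant, nominal schedule**

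| Last injection | 4 mg days | 6 mg days | Column |
|---|---|---|---|
| Week 3 | 14 | 0 | 6 mg (titration exception) |
| Week 4 | 14 | 7 | 4 mg |
| Week 5 | 14 | 14 | 6 mg (tie rule) |
| Week 6 | 14 | 21 | 6 mg |

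The 14 days at 2 mg belong to no group and are left out. If they were credited to 4 mg, the 4 mg total would be 28 days. One to three 6 mg injections (7, 14 or 21 days) would then go to 4 mg, and four (28 days) would tie to 6 mg.

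**Visit windows.** Time at 4 mg is (28 ±3) − (14 ±3), that is 8 to 20 days.
- One 6 mg injection (7 days): always fewer than the 4 mg days, so the Week 4 result does not change.
- Two (14 days): can lose if the windows stretch 4 mg time beyond 14 days.
- Three (21 days): never lose.

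**Re-titration.** Protocol 7.1.2.1 has titration re-initiated after three or more consecutive missed doses. Take a participant who reaches 6 mg at Week 4, misses Weeks 5 to 7, receives 2, 2, 4, 4, 6 mg at Weeks 8 to 12 and stops. At 7 days per injection this is 4 × 7 = 28 days at 4 mg and 2 × 7 = 14 at 6 mg, so the column is 4 mg. After one or two missed doses, the protocol lets treatment restart at the last dose given and does not set out the later step-up. The SAP's exposure formula also runs "regardless of unplanned intermittent discontinuations". How many stopping points are affected after a restart therefore depends on choices the documents do not make, and no count is offered.

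**Scale.** Assume 300 per column and k moved participants who all stopped for an adverse event, with x6 and x4 such events before the move. The fall in the 6 mg minus 4 mg difference is

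(x6/300 − x4/300) − [(x6 − k)/(300 − k) − (x4 + k)/(300 + k)].

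For 10% v 5% and k = 1: 30/300 − 15/300 = 5.0 points becomes 29/299 − 16/301 = 9.70 − 5.32 = 4.38 points, a fall of about 0.62. Over assumed rates of 3–20% (6 mg) and 2–15% (4 mg), the fall is 0.55 to 0.65 for k = 1 and 1.65 to 1.95 for k = 3. The 6 mg rate alone falls by 0.27 (60/300 to 59/299) to 0.32 (9/300 to 8/299) points per person, so contrasts with dulaglutide move slightly too.

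**The case against.** Four points can be made for the SAP as written.

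1. **The titration exception may cover the case.** Protocol 6.6 describes up-titration as running to Week 4, and Table 2 lists the Week 4 dose in the same schedule. SAP 2.4.5.2 labels the first 4 weeks as the titration period, though only for hypoglycemia. If that cut were borrowed and the stop dated by the last injection, a Visit 5 injection on Day 25 to 28 would stay in 6 mg and one on Day 29 to 31 would not. This stands as an ambiguity. A reader might infer that the SAP definitely places this participant under 4 mg, but the text does not settle it.

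2. **Treatment group may mean the randomized regimen.** SAP 1.1 lists the groups as the randomized arms, and Protocol 4.3 calls 2 mg the starting dose of both efpeglenatide groups. On that reading nobody moves. The titration exception would still have a purpose, because the two arms receive identical doses through Week 3. Only the dulaglutide sentence would be surplus, and it could be a clarification. The reading is possible, but the dulaglutide sentence and the reference to duration make dose-level counting the more natural one.

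3. **Other outputs carry part of the signal.** SAP 2.2 gives reasons for treatment discontinuation by group with randomized denominators, and Kaplan-Meier incidence of stopping for an adverse event. The PROMIS gastrointestinal scales are summarized on the ITT population. The adverse event listings show study day, exposure duration and action taken. This stands and limits the consequence.

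4. **Safety is descriptive.** SAP 2.4.5 plans no systematic testing. This also stands.

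**Conclusion.** The gap is real and minor. On dose-level counting, SAP 2.3.2 would place a compliant 6 mg participant who stops after the first 6 mg injection under 4 mg, while keeping one who stops a dose earlier under 6 mg. Some participants who re-titrate or restart and then stop soon after reaching 6 mg could be affected in the same way. Whether any of this happens depends on how a programmer reads two undefined terms.

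On the nominal schedule and with full compliance, one stopping week is at issue. The number of participants is not given and is probably very small. The percentage-point shifts rest on assumed event rates and column sizes, and show only what one or three moved participants would do.

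A reader might infer that the 6 mg safety profile is materially understated or that the trial's conclusions are at risk. The documents do not support that. The effect is confined to descriptive as-treated safety, exposure and compliance tables, in both efpeglenatide columns. Efficacy is analyzed as randomized and does not change.

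**What to change.** Add one sentence to SAP 2.3.2, next to the dulaglutide rule:

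> When calculating efpeglenatide treatment duration, 2 mg and 4 mg injections given under the titration schedule, including any restart or re-titration under protocol Section 7.1.2.1, will be combined with the randomized efpeglenatide dose; injections from kits dispensed in error remain under the longer-exposure rule.

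The Week 4 stopper then has 14 + 14 + 7 = 35 days under 6 mg and none under 4 mg. The re-titration example also stays in 6 mg. No separate definition of the titration phase is needed.

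The cost is one SAP edit before database lock. SAP version 2, dated 2 October 2020 and so after the 9 September 2020 termination, already revised this definition. Nothing changes for kits, randomization, visits or participants, and no protocol amendment is proposed. The downside is that a participant with more weeks at 4 mg than at 6 mg is reported under 6 mg. The dulaglutide rule already accepts the equivalent for 0.75 mg.

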### **4.3 JUSTIFICATION FOR DOSE**

The selection of efpeglenatide 4 mg and 6 mg once-weekly doses is based on the results of early phase studies.

Efpeglenatide has shown increasing efficacy up to the highest dose tested. The once-weekly 4 mg dose has shown clinically relevant efficacy (studies HM-EXC-202 and HM-EXC-203). The once-weekly 6 mg dose tested in non-diabetic subjects in the Phase 2 study (HM-EXC-205) has shown higher efficacy in the decrease of body weight than the once-weekly 4 mg dose in this population. Most likely, higher efficacy of the 6 mg dose compared to the 4 mg dose can also be expected for glycemic control in diabetic patients.

Nausea and vomiting events appeared to be dose related and the trend over time showed an increase in incidence after the first injection with a general decrease thereafter for all tested doses. The 2 mg dose demonstrated good GI tolerability has been selected as the starting dose of both, the 4 and 6 mg efpeglenatide treatment groups in this study. Based on the observed general decrease of GI event incidence after the first week of treatment with efpeglenatide, dose increases to achieve 4 and 6 mg (in the corresponding arm) will be in 2 mg step intervals every 2 weeks in order to minimize the GI adverse effects. The escalation step of 2 mg is small enough to contribute to improvement of GI tolerability at dose increase. With this dose escalation schedule, the dose of 4 mg once-weekly will be achieved 2 weeks and the maximal dose of 6 mg once-weekly will be achieved only 4 weeks after the first dose of efpeglenatide.

Dulaglutide will be administered at 1.5 mg once weekly, as per approved label following an initiation to be started at 0.75 mg once weekly (5).

Please refer to the IB for more details (2).

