**Dosing instructions**

The injection interval of the IMP is once weekly, preferably on the same week day (eg, each Monday) at any time of the day. Injections should be administered SC to any of the following body regions: abdomen, thigh, or upper arm. Within any selected region, the site of injection should be changed (rotated) at each time to prevent skin reactions. The region, date, and time of administration should be recorded for each injection administered.

For selected visits during the Treatment Period up to Week 30 (corresponding to predose PK sample collection) the weekly dose will be administered at the study site after blood sample collection (see SoA, [Section 1.3](#)).

For the other weekly administrations, if a dose is missed, participants must be instructed to administer it as soon as possible if there are at least 3 days (72 hours) until the next scheduled dose. If less than 3 days remain before the next scheduled dose, the participant should skip the missed dose and administer the next dose on the regularly scheduled day. In each case, participants can then resume their regular once-weekly dosing schedule. The day of weekly administration can be changed if necessary as long as the last dose was administered 3 or more days before (see [Section 7.1.2.1](#)).

Participants will be asked to administer the last 2 consecutive weekly dose injections prior to PK sampling at the same body region (eg, at Week 2 and Week 3 before the planned PK visit at Week 4; see [Section 8.5](#)).

Predose PK samples are expected to be collected at least 6 to 7 days after last dose of IMP. The corresponding study visits (Visit 5, Visit 7, Visit 9 and Visit 10) and the timing of dose administration before each of these visits should be scheduled to ensure, as much as possible, the duration of 6 to 7 days between them is maintained.

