**IMP dose schedule**

	Dose 1	Dose 2	Dose 3	Dose 4	Dose 5
	Day 1	Week 1	Week 2	Week 3	Week 4
	Visit 3		Visit 4		Visit 5
Dosing	(on-site)	(at home)	(on-site)	(at home)	(on-site)
Epeglenatide 4 mg	2 mg	2 mg	4 mg	4 mg	4 mg
Epeglenatide 6 mg	2 mg	2 mg	4 mg	4 mg	6 mg
Dulaglutide 1.5 mg	0.75 mg	0.75 mg	1.5 mg	1.5 mg	1.5 mg

From Week 4 (Visit 5) through the rest of the treatment period, participants will remain on the randomized IMP dose until the EOT at Week 56 (Visit 14).

**Storage conditions** Store between +2°C and +8°C (36°F and 46°F). Do not freeze, protect from light.

**Packaging and labeling** Study treatment will be provided in boxes, in accordance with the administration schedule. The content of the labeling is in accordance with the local regulatory specifications and requirements.

The details of this table are specific to IMP; information of non-IMP is described separately in this [Section 6.1.2](#).

EOT: end of treatment, IMP: investigational medicinal product, PK: pharmacokinetics, SC: subcutaneous, SoA: schedule of activities

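### Does pooling titration days for dulaglutide only, in SAP 2.3.2, put 6 mg participants in the 4 mg safety column?

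*SAP*

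**What the plan says.** SAP 2.3.2 analyses the safety population by treatment actually received. A participant "will be included in the treatment group that they are exposed for longer duration", and a tie goes to the highest efpeglenatide dose group. For the comparator it adds that "the Dulaglutide 0.75 mg duration will be combined with Dulaglutide 1.5 mg". No sentence says how efpeglenatide titration days count. A separate bullet makes an exception for early stops: "Participants, who premature discontinued study treatment during the titration phase, will be summarized in their planned treatment group for as-treated analysis too". Section 2.3.2 does not say when titration ends.

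In Protocol Table 2 the 6 mg group receives 2, 2, 4 and 4 mg, then 6 mg from the fifth dose; the 4 mg group receives 2, 2, 4 and 4 mg, then 4 mg. The table adds: "From Week 4 (Visit 5) through the rest of the treatment period, participants will remain on the randomized IMP dose". SAP 2.4.5.2 labels the first 4 weeks, inclusive, as the titration period for the hypoglycemia summaries. SAP 2.4.3.1 defines exposure as last dose date minus first dose date plus 7 days, "regardless of unplanned intermittent discontinuations".

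**The concern.** The two drugs look unequally treated. Dulaglutide 0.75 mg is used only for titration, so pooling it is almost a formality. Efpeglenatide 4 mg is a titration step in one arm and the maintenance dose of another, so it is the case that needs a sentence and has none. Read literally by dose level, a participant who followed the 6 mg schedule exactly could be tabulated under 4 mg.

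Those who could move are not a random sample. Protocol 2.3 and 4.3 describe nausea and vomiting as dose related, and Protocol 7.1.1 lists confirmed intolerance of the allocated dose as a reason to stop. Someone who stops just after the first 6 mg injection may have had the very event that the safety tables compare. The move would take that event out of the 6 mg column, add it to the 4 mg column, and narrow the dose contrast.

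**Working it through.** **Inputs.** Dose schedule: Protocol Table 2. Duration formula: SAP 2.4.3.1, here applied to each dose level separately. The SAP defines it only for overall exposure, so this is an assumption. Tie rule: SAP 2.3.2. Visit 5 window: Day 28 ±3 (Protocol 1.3). The SAP gives no figure of its own to reproduce.

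**Day count, exact weekly dosing from Day 1.**

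- 4 mg on Days 15 and 22: 22 − 15 + 7 = 14 days.
- One 6 mg injection, Day 29: 7 days. 14 > 7, so 4 mg.
- Two, Days 29 and 36: 36 − 29 + 7 = 14. A tie, so 6 mg.
- Three: 21 > 14, so 6 mg.
- With efpeglenatide pooled as dulaglutide is, one 6 mg injection gives 14 + 14 + 7 = 35 days, all under 6 mg.

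**Off-schedule dosing.** The injection day may be changed "as long as the last dose was administered 3 or more days before".

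- 4 mg doses 3 days apart: 3 + 7 = 10, still more than 7.
- One 4 mg dose missed: 7 against 7, a tie, so 6 mg.
- Second 4 mg dose one day late (Days 15 and 23): 8 + 7 = 15, which exceeds the 14 days of two weekly 6 mg injections. A two-injection participant can therefore move too.
- If 4 mg time is instead the span from Visit 4 (Day 14 ±3) to Visit 5, it runs from 8 to 20 days. One 6 mg injection is shorter in all 49 day combinations, two are shorter in 21 of 49, and three in none.

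**Condition 1: is exposure counted by dose level?** The rule refers to treatment group, and SAP 1.1 lists three: efpeglenatide 4 mg, efpeglenatide 6 mg and dulaglutide 1.5 mg. Table 2 shows the two 4 mg injections as part of the 6 mg group's own row. Protocol 4.3 says that 2 mg "has been selected as the starting dose of both, the 4 and 6 mg efpeglenatide treatment groups". A 2 mg injection thus cannot be assigned to a group by its strength; the regimen has to be consulted. On regimen counting, nobody who follows the schedule moves.

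**Condition 2: does the exception miss the fifth dose?** With exact weekly dosing the fifth dose is on Day 29, which is 29 − 1 = 28 elapsed days, or 4 weeks. A stop dated to that injection lies within an inclusive 4-week titration period, and the participant stays under 6 mg. If 4 weeks is read as study Day 28, Days 25 to 28 of the Visit 5 window (4 of 7) are inside and Days 29 to 31 (3 of 7) outside. If the stop is dated later than the last injection, the exception may not apply.

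**Effect of one participant moved.** Assume 300 treated per arm and illustrative event counts of 24 (6 mg) and 15 (4 mg), a difference of 3.00 points.

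- With the event: 23/299 − 16/301 = 7.69% − 5.32% = 2.38 points (−0.62).
- Without it: 24/299 − 15/301 = 8.03% − 4.98% = 3.04 points (+0.04).
- From 15 against 15: 14/299 − 16/301 = −0.63 points with the event; 15/299 − 15/301 = +0.03 without.

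**The case for a change.** The best case for acting is that the text points towards dose-level counting. If exposure were counted by regimen, 0.75 mg days would already belong to dulaglutide, the pooling sentence would do nothing, and the titration bullet would be largely unnecessary. A programmer could reasonably infer that efpeglenatide strengths are not pooled. The boundary is also open, so two programmers could code a fifth-dose stop differently. Re-titration after three or more missed efpeglenatide doses (Protocol 7.1.2.1) adds 4 mg days that the rule does not mention. The shifts add up, too: on the illustrative counts, five movers who all had the event would cancel the 3-point difference (19/295 − 20/305 = −0.12 points).

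Much of this stands. The wording is incomplete, and the day count is right on its premises. It does not establish an error, because both conditions must hold and the text supports the other reading of each at least as well. The two sentences cited as evidence for dose-level counting also show the purpose: each keeps scheduled titration from deciding the column. An analyst facing a fifth-dose stop has that purpose, the regimen rows in Table 2 and an inclusive 4-week label to work from. The number of movers cannot be derived from the documents. Several movers sharing one event would have to come from the few who stop within an injection or two of reaching 6 mg.

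**Conclusion.** No change to the plan follows. SAP 2.3.2 leaves two details unwritten: how scheduled efpeglenatide titration days count, and on which side of the titration boundary the fifth dose falls. These are details that analysts settle in programming, and the surrounding text points to a sensible answer. Under regimen counting, or if the exception covers the fifth dose, the number misplaced is zero.

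On the least favourable reading, those affected are 6 mg participants who stop after one 6 mg injection, some who stop after two when doses ran late, and possibly some who were re-titrated. Each would shift a 6 mg minus 4 mg difference by about 0.6 points for an event they had, assuming 300 treated per arm. SAP 2.4.5 makes the safety analysis essentially descriptive with no systematic testing, so no formal conclusion depends on it. Efficacy, PROMIS and disposition summaries use randomized groups and are unaffected. The listings of serious events, events leading to discontinuation and other selected events carry duration of exposure, so such a participant could be recognised there.
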